**EFFECT OF VITAMIN D3 SUPPLEMENTATION ON HEPSIDIN AND FERRITIN SERUM
LEVELS IN CHILDREN WITH CHRONIC KIDNEY DISEASE**

May 1st 2023

EFFECT OF VITAMIN D3 SUPPLEMENTATION ON HEPSIDIN AND FERRITIN SERUM LEVELS IN CHILDREN WITH CHRONIC KIDNEY DISEASE

Protocol

Responsible Personnel

Principal Investigator Contact Information

Name: [name]

Title: MD

Institution: Department of Pediatrics, Faculty of Medicine, Hasanuddin University

Address: [name]

[contact]

Email: [contact]

Summary:

This study aim to assess the effect of Vitamin D administration on Hepcidin and Ferritin serum level in children with chronic kidney diseases. It is a clinical trial involving 43 chronic kidney disease patients at [name] Hospital in Makassar, Indonesia. Subjects are enrolled into two different groups, one with glomerulus filtration rate (GFR) more than 90 mL/min/1,73 m² and the other group consist of children with GFR less than 90 mL/min/1,73 m². Both group will be given the same dose of Vitamin D, which is 2000 IU for 6 weeks. Measurements of vitamin D, hepcidin and ferritin level will be before and after Vitamin D supplementation.

Introduction:

Chronic kidney disease (CKD) is a significant global health issue characterized by a gradual decline in kidney function over time. Defined by the Kidney Disease: Improving Global Outcomes (KDIGO) guidelines, CKD involves abnormalities in kidney structure or function lasting more than three months, which can lead to complications such as anemia. In children, CKD can adversely affect growth patterns and is closely linked to anemia due to reduced erythropoietin production, which disrupts iron homeostasis essential for oxygen transport in the body.

Anemia in CKD patients is primarily driven by iron deficiency, with studies indicating that the incidence ranges from 7.2 to 13.96 per 1,000 people annually, contributing to approximately 800,000 deaths globally. In pediatric populations, the prevalence of anemia among children with CKD is notably high, affecting 36-58% of patients in regions like the United States and Germany. The increasing incidence of CKD in children is likely related to longer life expectancy and improved treatment options, although data on early-stage CKD remain limited.

Vitamin D deficiency is another critical issue associated with CKD, particularly in children. Research shows that a significant percentage of patients undergoing hemodialysis exhibit low vitamin D levels, which can exacerbate anemia by lowering hemoglobin levels. Vitamin D plays a vital role in erythropoiesis, and its deficiency correlates with increased serum hepcidin levels—a hormone that regulates iron metabolism and can hinder iron absorption and release from stores.

Given the interconnectedness of vitamin D levels, hepcidin concentration, and anemia in children with CKD, research is warranted to explore the effects of vitamin D supplementation on serum hepcidin and ferritin levels. There is currently a lack of studies addressing this relationship,

especially in Indonesia. This research aims to fill the gap in knowledge regarding vitamin D's potential benefits for managing anemia and iron homeostasis disorders in pediatric CKD patients.

Objectives of Trial:

1. **Primary Objective**
 - a. To assess the effect of Vitamin D supplementation on hepcidin and ferritin serum level in children with CKD
2. **Secondary Objective**
 - a. To assess vitamin D, hepcidin, and ferritin level in children with CKD and GFR less than 90 ml/min/1,73 m² before vitamin D3 supplementation
 - b. To assess vitamin D, hepcidin, and ferritin level in children with CKD and GFR more than 90 ml/min/1,73 m² before vitamin D3 supplementation
 - c. To assess vitamin D, hepcidin, and ferritin level in children with CKD and GFR less than 90 ml/min/1,73 m² after vitamin D3 supplementation
 - d. To assess vitamin D, hepcidin, and ferritin level in children with CKD and GFR more than 90 ml/min/1,73 m² after vitamin D3 supplementation
 - e. To compare vitamin D, hepcidin, and ferritin level in children with CKD and GFR less than 90 ml/min/1,73 m² before and after vitamin D3 supplementation
 - f. To compare vitamin D, hepcidin, and ferritin level in children with CKD and GFR more than 90 ml/min/1,73 m² before and after vitamin D3 supplementation
 - g. To compare vitamin D, hepcidin, and ferritin level between children with GFR less than 90 ml/min/1,73 m² and children with GFR more than 90 ml/min/1,73 m² before vitamin D3 supplementation
 - h. To compare vitamin D, hepcidin, and ferritin level between children with GFR less than 90 ml/min/1,73 m² and children with GFR more than 90 ml/min/1,73 m² after vitamin D3 supplementation

Hypothesis:

1. Serum hepcidin level is lower after vitamin D3 supplementation in children with CKD
2. Serum ferritin level is lower after vitamin D3 supplementation in children with CKD
3. Serum hepcidin level is lower in pediatric CKD patients with GFR more than 90 ml/min/1,73 m² compare to GFR less than 90 ml/min/1,73 m²
4. Serum ferritin level is lower in pediatric CKD patients with GFR more than 90 ml/min/1,73 m² compare to GFR less than 90 ml/min/1,73 m²

Study Design:

Interventional study

Study Population:

Number of samples:

43 subjects

Inclusion criteria:

- Patients aged 2 to 18 years diagnosed with chronic kidney diseases at [name] hospital
- Parents have signed their child's consent to participate in the study

Exclusion criteria:

- History of blood transfusion 3 months prior
- Liver dysfunction
- Sepsis
- Routine consumption of Vitamin D
- Routine consumption of iron supplement
- Patients diagnosed with iron deficiency anemia

Product Description:

Vitamin D3 with the dose of 2,000 IU

Outcomes:

The primary outcomes being measured in this study are serum vitamin D levels, serum hepcidin levels and serum ferritin levels. These outcomes will be measured in children with CKD before and after 6 weeks of vitamin D3 supplementation. We plan to compare these levels in two groups of CKD patients - those with glomerular filtration rate (GFR) <90 mL/min/1.73 m² and those with GFR ≥ 90 mL/min/1.73 m². Measurement will be done by collecting 3 ml of blood to measure the level of vitamin D, hepcidin and serum ferritin.

Statistical analysis will utilize unpaired T test or Mann-Whitney test will be used to compare vitamin D, hepcidin and ferritin serum level in subjects according to the distribution of the data. Paired T Test or McNemar test will also be used to compare proportion of individually matched event for the two groups before and after vitamin D3 supplementation. Lastly, Pearson or Spearman test will be done to assess the correlation between vitamin D level and hepcidin and ferritin serum level.

Conduct of Trial:

This study will be conducted as a clinical trial involving children with chronic kidney disease (CKD). Participants will be divided into two groups based on their glomerular filtration rate (GFR): those with GFR <90 mL/min/1.73 m² and those with GFR ≥ 90 mL/min/1.73 m². All participants will undergo initial blood tests to measure serum levels of vitamin D, hepcidin, and ferritin. Following these baseline measurements, the children will receive vitamin D3 supplementation for a specified period. After the supplementation period, blood tests will be repeated to measure the same parameters. We will then compare the pre- and post-supplementation levels of vitamin D, hepcidin, and ferritin within each GFR group, as well as between the two GFR groups. This approach will allow us to assess the effect of vitamin D3 supplementation on serum hepcidin and ferritin levels in children with CKD, and to determine if the effect differs based on the severity of kidney dysfunction as indicated by GFR.

[figure not shown]

Figure 1. Study Procedure

Statistical Aspects and Considerations:

This study employs a comprehensive statistical approach to analyze the effect of vitamin D3 supplementation on serum hepcidin and ferritin levels in children with chronic kidney disease (CKD). We will utilize both descriptive and inferential statistics to examine their data. Descriptive statistics will be used to summarize the categorical data as counts and ratios, while quantitative

data will be presented as mean values with standard deviation. For inferential statistics, the study will employ Pearson's correlation test to differentiate between groups and assess statistical significance. The significance level is set at $P < 0.05$ for statistical significance and $P < 0.01$ for high significance. The statistical analysis will be conducted using SPSS version 20.0. Important considerations for this study include ensuring an adequate sample size to detect clinically meaningful differences, which will be determined through a sample size calculation. We will account for potential confounding variables, assess whether assumptions are met for the planned statistical tests, handle any missing data appropriately, and conduct sensitivity analyses to evaluate the robustness of results. By addressing these statistical aspects and considerations, our study aims to produce valid and reliable results regarding the effects of vitamin D3 supplementation on serum hepcidin and ferritin levels in children with CKD, comparing outcomes between groups with different glomerular filtration rates ($\text{GFR} < 90 \text{ mL/min/1.73 m}^2$ and $\text{GFR} \geq 90 \text{ mL/min/1.73 m}^2$).

References

Altemose, K. E., Kumar, J., Portale, A. A., Warady, B. A., Furth, S. L., Fadrowski, J. J., & Atkinson, M. A. (2018). Vitamin D insufficiency, hemoglobin, and anemia in children with chronic kidney disease. *Pediatric Nephrology*, 33(11), 2131–2136. <https://doi.org/10.1007/s00467-018-4020-5>

Avner, E. D., Harmon, W. E., Niaudet, P., Yoshikawa, N., Emma, F., & Goldstein, S. L. (Eds.). (2016a). *Pediatric Nephrology*. Springer Berlin Heidelberg. <https://doi.org/10.1007/978-3-662-43596-0>

Avner, E. D., Harmon, W. E., Niaudet, P., Yoshikawa, N., Emma, F., & Goldstein, S. L. (Eds.). (2016b). *Pediatric Nephrology*. Springer Berlin Heidelberg. <https://doi.org/10.1007/978-3-662-43596-0>

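### Baseline vitamin D is measured in every child, but no fixed analysis relates it to the hepcidin or ferritin change or adjusts the GFR comparison for it

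*Protocol*

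**What the plan says.** The Introduction links vitamin D to hepcidin through deficiency: "its deficiency correlates with increased serum hepcidin levels". The primary objective is wider: "To assess the effect of Vitamin D supplementation on hepcidin and ferritin serum level in children with CKD". The first hypothesis is equally general: "Serum hepcidin level is lower after vitamin D3 supplementation in children with CKD".

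Under Study Population, the inclusion criteria are "Patients aged 2 to 18 years diagnosed with chronic kidney diseases" at the study hospital, and signed parental consent. No criterion refers to a serum vitamin D level. The only vitamin D rule is the exclusion "Routine consumption of Vitamin D", which concerns supplement use.

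Under Conduct of Trial, "All participants will undergo initial blood tests to measure serum levels of vitamin D, hepcidin, and ferritin". The same section says that the design will show whether the effect differs with the severity of kidney dysfunction, as measured by GFR.

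The Outcomes section names unpaired t or Mann-Whitney tests, paired t or McNemar tests, and a correlation: "Lastly, Pearson or Spearman test will be done to assess the correlation between vitamin D level and hepcidin and ferritin serum level". Statistical Aspects and Considerations adds Pearson's correlation, and general undertakings on confounding and sensitivity analyses that name no variable.

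**The concern.** If vitamin D works on hepcidin by correcting a deficiency, the natural question is whether children who start lower respond more. The data for that question will exist, but no fixed analysis asks it.

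Two readings of the results are at stake:

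- **A null pooled change.** It could mean that supplementation does not lower hepcidin, or that a good share of the children had little to correct. The planned tests do not separate these.
- **A difference between GFR groups.** The groups are formed by kidney function, not by randomisation, and secondary objective (g) itself compares their baseline vitamin D. If they differ, an apparent GFR difference in response may partly be a difference in starting vitamin D. None of the named tests adjusts for a covariate.

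**Working it through.** **Does any fixed analysis do the job?**

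| Planned analysis | Use of vitamin D | Relates the marker change to baseline vitamin D? |
|---|---|---|
| Before-after tests within GFR group (objectives e, f) | an outcome | No |
| GFR groups compared before, and again after (objectives g, h) | an outcome | No; these compare levels, not change |
| Pearson or Spearman correlation | level against marker level, time point not stated | No |
| Claim that the effect differs by GFR (Conduct of Trial) | not used | No test of change and no adjustment is named |

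**How much could dilution matter?** The protocol gives 43 subjects and a 0.05 significance level. It gives no effect size, SD, power or deficient share, so there is no stated power figure to reproduce.

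Assumptions:
- two-sided test;
- a share q of children is deficient;
- deficient children change by d, in units of the within-stratum SD of the paired difference;
- replete children change by 0;
- all 43 children are analysed.

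Formulas:
- Pooled mean change = q × d.
- Pooled SD = √(1 + q(1 − q)d²).
- Standardised effect e = mean / SD.
- Power from the noncentral t with 42 degrees of freedom and noncentrality e√43.

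Example with q = 0.5 and d = 0.5: mean 0.25; SD √(1 + 0.25 × 0.25) = 1.031; e = 0.243; noncentrality 0.243 × 6.557 = 1.59; power 34%.

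| q (deficient) | d | e | Pooled power, n = 43 |
|---|---|---|---|
| 100% | 0.5 | 0.50 | 89% |
| 90% | 0.5 | 0.45 | 81% |
| 75% | 0.5 | 0.37 | 65% |
| 50% | 0.5 | 0.24 | 34% |
| 25% | 0.5 | 0.12 | 12% |
| 75% | 0.8 | 0.57 | 95% |
| 50% | 0.8 | 0.37 | 66% |

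The loss runs from small to severe, depending on inputs that the protocol does not state.

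**GFR comparison (illustration only).** Suppose 80% of one group and 40% of the other are deficient, and deficient children respond by the same 0.5 SD in both. The mean changes are 0.8 × 0.5 = 0.40 SD and 0.4 × 0.5 = 0.20 SD. The unadjusted difference of 0.20 SD comes entirely from baseline vitamin D.

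**What could the data show about modification?** A two-sample t test of change in deficient against replete children, d = 0.5, has power 29%, 36% and 29% at 75%, 50% and 25% deficient (32/11, 22/21 and 11/32 children). A before-after test in the deficient children alone has 78%, 61% and 32% (32, 22 and 11 children).

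**The case against.** The strongest objection is that the objective and hypotheses concern children with CKD as a whole, so the mean over all of them is the quantity sought. That stands. A reader might infer that replete children bias the primary result, or that enrolling them contradicts the rationale. The documents support neither: the Introduction reports a correlation, and the objective is not limited to deficient children.

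A reader might also infer that dilution is certain. It is not. The deficient share is not given, and zero response in replete children is an assumption, not a statement of the protocol. Excluding routine vitamin D users probably lowers the replete share, though it does not guarantee deficiency.

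A third objection is that a covariate analysis may sit in a statistical analysis plan that is not shown, and that the protocol already undertakes to deal with confounding. This limits the weight of the point but does not remove it. The protocol does fix its tests and makes a specific claim about GFR, and the tests it fixes cannot carry that claim with adjustment.

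Lastly, objective (g) would reveal a baseline vitamin D imbalance, and objectives (e) and (f) would show whether levels rose. Both help interpretation, but neither separates GFR from baseline vitamin D. The low power for modification also stands, which is why that result can only be supportive.

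**Conclusion.** The point holds as a gap between the questions the protocol raises and the analyses it fixes. It is not an error in the primary estimate. Baseline vitamin D is available for every child, yet it is not related to the marker change and does not enter the GFR comparison. The gap matters most for that comparison, because the groups are not randomised.

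The effect on the pooled test cannot be given as one figure. On the assumptions shown, power with 43 children ranges from 95% (75% deficient, 0.8 SD) to 34% (50% deficient, 0.5 SD), and falls to 12% if only 25% are deficient at 0.5 SD. With few replete children or a large effect, little is lost. The improvement is worth making because it costs almost nothing and is credible only if fixed before the data are seen.

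**What to change.** Leave enrolment and the before-after tests as they are. In the Outcomes section and in Statistical Aspects and Considerations, add one pre-specified linear regression for each marker. The dependent variable is the 6-week change in hepcidin or in ferritin. The covariates are GFR group, the marker's own baseline value, and baseline vitamin D as a continuous variable. Base any claim that the response differs by GFR on the GFR coefficient from this model. Report the baseline vitamin D coefficient as supportive evidence on response by vitamin D status.

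State also that a null pooled change will not be read as ruling out an effect in deficient children. A before-after estimate in deficient children alone is optional. If given, it should be labelled exploratory, use a cut-off fixed in advance, and carry a warning about regression to the mean, since those children are selected on a low baseline measurement.

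The cost is one further analysis per marker on data already planned, with no new samples or patients. The drawback is low power: at 0.5 SD, about 29% to 36% for a deficient-against-replete comparison when 25% to 75% are deficient. A non-significant vitamin D coefficient would therefore settle little.

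### Serum vitamin D is listed as a primary outcome although the primary objective covers only hepcidin and ferritin, and the whole-cohort before–after comparison that the objective asks for is never named

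*Protocol*

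**What the plan says.** The protocol sets its priority in three places that agree.

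- Summary: "This study aim to assess the effect of Vitamin D administration on Hepcidin and Ferritin serum level in children with chronic kidney diseases".
- Objectives of Trial, the only primary objective: "To assess the effect of Vitamin D supplementation on hepcidin and ferritin serum level in children with CKD".
- Hypothesis 1: "Serum hepcidin level is lower after vitamin D3 supplementation in children with CKD". Hypothesis 2 says the same of ferritin.

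Under Objectives of Trial, vitamin D level occurs only in secondary objectives a to h. The before–after comparisons within each GFR group are secondary objectives e and f; objective e begins "To compare vitamin D, hepcidin, and ferritin level in children with CKD and GFR less than 90". The comparisons of levels between GFR groups, before and then after supplementation, are secondary objectives g and h. Hypotheses 3–4 concern differences between GFR groups and stand beside Hypotheses 1–2 without a ranking. No hypothesis concerns vitamin D level.

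Later sections read differently.

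- Outcomes: "The primary outcomes being measured in this study are serum vitamin D levels, serum hepcidin levels and serum ferritin levels". Shortly after, it adds "We plan to compare these levels in two groups of CKD patients".
- Conduct of Trial: the investigators will "compare the pre- and post-supplementation levels of vitamin D, hepcidin, and ferritin within each GFR group, as well as between the two GFR groups". The next sentence opens "This approach will allow us to assess the effect of vitamin D3 supplementation on serum hepcidin and ferritin levels in children with CKD" and goes on to ask whether the effect depends on the severity of kidney dysfunction.
- Statistical Aspects and Considerations again couples the effect in children with CKD to a comparison of outcomes between the GFR groups.

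**The concern.** The priority set in the objectives is not carried into the sections that say what is primary and what will be compared. There are two consequences.

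First, vitamin D is the substance being given. A rise in its serum level shows that the supplement was taken and absorbed; it says nothing about hepcidin or ferritin. With three unranked primary outcomes, the trial could report a positive primary result on vitamin D alone while both iron markers stay flat.

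Second, Hypotheses 1–2 are about all children with CKD, but the comparison that answers them is not named. If hepcidin falls significantly in one GFR group and not in the other, the text does not say whether Hypothesis 1 is supported. The contrast between groups cannot settle it, because both groups receive the same supplement (Summary).

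**Working it through.** The finding rests on the text. The only design figure is 43 children. It cannot be reproduced, because the protocol gives no effect size, SD, power, group sizes or sidedness. The arithmetic below only shows what the choice of comparison costs.

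**Side by side**

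| Item | Summary, objectives, Hypotheses 1–2 | Outcomes, Conduct of Trial, Statistical Aspects |
|---|---|---|
| Primary markers | Hepcidin, ferritin | Vitamin D, hepcidin, ferritin (Outcomes) |
| Population | Children with CKD, undivided | Measured in children with CKD; comparisons described by GFR group |
| GFR-group comparisons | Secondary (e to h) | Given as the way the effect is assessed |
| Whole-cohort before–after comparison | Implied by the primary objective | Not named, not excluded |

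The Outcomes sentence on the paired test speaks of two groups, before and after. That can mean the two GFR groups or the two sets of measurements, so it does not settle the matter.

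**Precision, no effect size assumed**

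Inputs: 43 children (Study Population), all assumed to complete; an assumed 22/21 split; two-sided 95% intervals. Half-width of the interval for a mean paired change, in SD of the change = t(0.975, n − 1)/√n.

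- n = 43: 2.018/6.557 = 0.308
- n = 22: 2.080/4.690 = 0.443
- n = 21: 2.086/4.583 = 0.455

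An uneven split widens the gap: with 33 and 10 children the half-widths are 0.355 and 0.715.

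**How often would the two groups disagree?** (illustration)

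Assume the same true effect in both groups, a 22/21 split, and paired t-tests at two-sided 0.05. With power p₁ and p₂, the chance that exactly one test is significant is p₁(1 − p₂) + p₂(1 − p₁).

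| True change (SD of the change) | p₁ (n = 22) | p₂ (n = 21) | Exactly one significant |
|---|---|---|---|
| 0.3 | 0.269 | 0.258 | 0.388 |
| 0.4 | 0.433 | 0.415 | 0.489 |
| 0.5 | 0.609 | 0.587 | 0.481 |
| 0.6 | 0.765 | 0.744 | 0.371 |

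For example, at 0.5 SD: 0.609 × 0.413 + 0.587 × 0.391 = 0.481. So split verdicts are common even when the groups respond identically.

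**What can answer whether the effect differs by GFR?**

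Secondary objectives e and f test change separately in each group. Objectives g and h compare levels at each time point. None of them compares the change between groups. The table shows why separate tests cannot stand in for that: one significant and one non-significant result arises 37% to 49% of the time with no difference in effect at all. The direct comparison is the difference between the groups' mean changes. With a common SD of the change, its 95% half-width is t(0.975, 41) × √(1/22 + 1/21) = 2.020 × 0.305 = 0.62 SD, which is wide but addresses the right quantity.

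**Where pooling loses**

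If one group changes by 0.6 SD and the other not at all, simulation (100,000 runs) gives the pooled test a power of 0.435 when the group of 21 responds and 0.468 when the group of 22 does. The responding group's own test has 0.744 and 0.765.

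**The case against.** The strongest reply has four parts.

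1. Hepcidin and ferritin are never in doubt. Every statement of purpose names them and the Outcomes section lists both as primary, so vitamin D's rank is a label on a list of three assays. This is partly right: measuring vitamin D is sound, and only its rank is at fault. But the rank decides what may be reported as a primary result.

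2. A reader might infer that the protocol replaces the whole-cohort test with GFR-group tests. The documents do not support that. Placing the within-group comparisons at secondary rank suggests that the primary objective means the whole cohort, the Outcomes section says the markers are measured before and after in children with CKD, and the Conduct of Trial sentence can be taken to refer to the whole procedure. This stands: the pooled comparison is unstated, not excluded. Test details may also sit in an analysis plan that is not shown. What remains is that the protocol's own sections do not agree on which comparison carries the primary question, and an analysis plan should inherit that ranking from the protocol.

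3. The GFR comparisons have a purpose of their own: Hypotheses 3–4 and the question of whether the effect depends on kidney function. This also stands. The GFR split is not the error. Yet leaving Hypotheses 3–4 unranked beside Hypotheses 1–2 makes the order of priority less clear.

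4. The conflict could be resolved the other way, by changing the primary objective. That would restore consistency, but it would move the aim, the objective and Hypotheses 1–2 to suit one sentence in the Outcomes section.

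**Conclusion.** The point holds in two limited parts. First, serum vitamin D is given primary status that the Summary, the primary objective and the hypotheses do not support. Second, the sections on outcomes, conduct and statistics do not name the whole-cohort before–after comparison that the primary objective and Hypotheses 1–2 ask for, and they present secondary comparisons as the route to that answer.

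Neither part depends on a calculation. The cost of relying on the group tests is a 95% half-width of 0.44 to 0.46 SD instead of 0.31 SD, if all 43 children are analysed and the split is 22/21. The disagreement rates and power figures further assume effect sizes that the protocol does not give, so they are illustrations. They do not show that pooling is always better: it has less power when only one group responds. Nor do they show that the trial is too small. The issue should be corrected before the data are analysed; it does not undermine the data collection.

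**What to change.** 1. In Outcomes, name hepcidin and ferritin as the primary outcomes and move serum vitamin D to secondary, in line with Objectives of Trial.
2. In Outcomes and Conduct of Trial, state that Hypotheses 1–2 are answered by the paired before–after change in hepcidin and ferritin in all 43 children, and bring Statistical Aspects and Considerations into line.
3. Keep secondary objectives e to h at their present rank, rank Hypotheses 3–4 as secondary too, and report the results of both GFR groups whatever the pooled result.
4. Answer the question of whether the effect differs by GFR by comparing the before–after change between the two groups, with its confidence interval. Do not infer it from separate within-group tests or from separate comparisons of levels before and after.

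The cost is wording only, with no extra children or blood samples. The drawback is the lower power of the pooled test if only one GFR group responds, which is why the group results should still be reported. Any multiplicity rule for the two primary markers can be left to the analysis plan.

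### The only test assigned to the before-after comparison is described as comparing a proportion of events, although the outcomes are continuous levels, no event is defined and no paired rank test is named

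*Protocol*

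**What the plan says.** The Outcomes section makes the endpoints continuous: "The primary outcomes being measured in this study are serum vitamin D levels, serum hepcidin levels and serum ferritin levels". The before-after question is put in terms of levels throughout:

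- Hypothesis 1: "Serum hepcidin level is lower after vitamin D3 supplementation in children with CKD". Hypothesis 2 says the same of ferritin.
- Objectives of Trial, secondary objective e: "To compare vitamin D, hepcidin, and ferritin level in children with CKD and GFR less than 90 ml/min/1,73 m² before and after" supplementation. Objective f repeats this for the higher-GFR group.
- Conduct of Trial: "We will then compare the pre- and post-supplementation levels of vitamin D, hepcidin, and ferritin within each GFR group".

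The Outcomes section then assigns tests in three sentences. The first covers unpaired comparisons: "unpaired T test or Mann-Whitney test will be used to compare vitamin D, hepcidin and ferritin serum level", with the choice made by how the data are distributed. The second covers the before-after comparison: "Paired T Test or McNemar test will also be used to compare proportion of individually matched event for the two groups". The third offers Pearson or Spearman for correlation.

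Statistical Aspects and Considerations names only Pearson's correlation, for telling groups apart. It also promises to "assess whether assumptions are met for the planned statistical tests".

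**The concern.** The sentence on the before-after comparison does not fit the data it is meant to analyse. A paired t-test compares means of paired measurements, not proportions. McNemar's test compares paired proportions, but it needs a yes/no event for each child at each visit. The protocol sets no deficiency threshold, cut-off or event for vitamin D, hepcidin or ferritin. Its only threshold, a GFR of 90, defines the groups.

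In the sentences on either side, the second test is the rank counterpart of the first: Mann-Whitney for the unpaired t-test, Spearman for Pearson. In the paired sentence McNemar's test stands where the Wilcoxon signed-rank test would be expected.

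Two readings are open, and each leaves a gap:

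- **Reading A.** McNemar's test replaces the paired t-test when the t-test is judged unsuitable. The levels must then be split at a cut-off that the protocol does not fix and that could be chosen after the data are seen. Power also falls.
- **Reading B.** The paired t-test is for levels and McNemar's test is for separate proportions. No event then exists for McNemar's test, and skewed levels have no named paired alternative.

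The primary objective and Hypotheses 1 and 2 depend on this comparison.

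**Working it through.** **Text check.** Each inferential statement in the protocol, set against the data type it needs:

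| Comparison | Tests named | Fits continuous levels? | Rank alternative? |
|---|---|---|---|
| Between GFR groups | Unpaired t / Mann-Whitney | Yes | Yes |
| Before vs after | Paired t / McNemar, said to compare a proportion | Paired t yes; McNemar and the description no | No |
| Correlation | Pearson / Spearman | Yes | Yes |
| Statistical Aspects section | Pearson's correlation, between groups | Not a before-after test | – |

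No other part of the protocol assigns a before-after test, and none names a signed-rank or sign test.

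**Inputs for the illustration.** From the protocol: 43 children and significance at P < 0.05. The protocol gives no effect size, SD, power or sidedness, so there is no power figure to reproduce. Assumed: two-sided testing; log levels bivariate normal before and after; log SD 0.8; a fall of 0.5 SD on the log scale; within-child correlation 0.7 or 0.5; 21 children in one GFR group (an equal split).

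**Method.** Simulation, 40,000 runs per setting. Level = exp(log SD × standardised log value). The paired t-test and exact Wilcoxon signed-rank test were run on untransformed levels. Exact two-sided McNemar was run at a cut at the baseline median, and at cuts 1 SD above and 1 SD below it.

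**Reading A: power if levels are dichotomised (log SD 0.8, fall 0.5 SD).**

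| n | Correlation | Wilcoxon | Paired t | McNemar, median cut | McNemar, +1 SD / −1 SD |
|---|---|---|---|---|---|
| 43 | 0.7 | 96.3% | 89.5% | 57.7% | 19.1% / 44.1% |
| 43 | 0.5 | 83.2% | 73.8% | 48.8% | 17.8% / 37.1% |
| 21 | 0.7 | 71.5% | 61.6% | 19.7% | 1.8% / 10.5% |
| 21 | 0.5 | 50.2% | 42.9% | 18.0% | 2.4% / 11.1% |

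Relative loss at the median cut = 1 − (McNemar power / Wilcoxon power):

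- n=43: 1 − 0.577/0.963 = 40% (correlation 0.7); 1 − 0.488/0.832 = 41% (0.5).
- n=21: 1 − 0.197/0.715 = 72% (0.7); 1 − 0.180/0.502 = 64% (0.5).

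The steep loss at n=21 has a simple cause. Exact McNemar uses only children who cross the cut. With five crossing, all in one direction, P = 2 × 0.5^5 = 0.0625; at least six are needed (2 × 0.5^6 = 0.031).

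**Sensitivity to effect size** (n=43, correlation 0.7, median cut, McNemar vs Wilcoxon):

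- Fall 0.3 SD: 22% vs 61%, a loss of 1 − 0.221/0.613 = 64%.
- Fall 0.5 SD: 58% vs 96%, a loss of 40%.
- Fall 0.8 SD: 94% vs 100%, a loss of 6%.

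**Reading B: Wilcoxon vs paired t on untransformed levels** (correlation 0.7, fall 0.5 SD):

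| Log SD | n=43 | n=21 |
|---|---|---|
| 0.5 | 97% vs 96% | 74% vs 73% |
| 0.8 | 96% vs 90% | 72% vs 62% |
| 1.1 | 95% vs 78% | 69% vs 48% |

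On log values the paired t-test has 98.5% power against 98.1% for Wilcoxon at n=43, and 80.1% against 77.3% at n=21.

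**Size under no effect.** Wilcoxon 4.6–5.0%, paired t on levels 4.2–4.5%, McNemar 0.2–2.7%. The fault costs power; it does not inflate false positives at a pre-set cut. A cut-off chosen after seeing the data was not simulated.

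**The case against.** The strongest reply is that the paired t-test is named, suits roughly normal differences, and makes the comparison testable. On this view the choice of a rank fallback, or of a cut-off, can be left to a statistical analysis plan, which may exist but is not shown. The protocol also promises assumption checks and sensitivity analyses. Nothing in the text says that McNemar's test is to replace the t-test for skewed data: the condition on the data's distribution is attached only to the unpaired sentence. Reading A is therefore an inference from the neighbouring sentences, and every McNemar figure depends on it. Under Reading B with mild skew the cost is about one percentage point.

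Much of this stands as a limit on size. Reading A is a possibility, not a stated plan. The loss at n=43 runs from 6% to 64% over the assumed falls, so 40% is one point in a range. A paired t-test on the log scale, fixed in advance, would serve at least as well as Wilcoxon under these log-normal assumptions.

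It does not remove the fault. The complaint is about what the protocol states, not about missing detail. An analysis plan that followed the sentence would have to invent an event, and one that named a signed-rank test would depart from it. The promised checks name no paired test to use if they fail.

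**Conclusion.** The concern holds as stated: the sentence is wrong as written and should be fixed. It describes a comparison of proportions for outcomes that are continuous, names a test for an event that is never defined, and gives the paired analysis no rank alternative. That conclusion rests on the text alone.

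The size is conditional. In the central case (fall 0.5 SD, log SD 0.8, correlation 0.7), reading McNemar's test as the fallback lowers power from 96% to 58% in the whole cohort and from 72% to 20% in one GFR group of 21. If it is not the fallback, the price of having only an untransformed paired t-test runs from about 1 percentage point (log SD 0.5) to 17 at n=43 and 21 at n=21 (log SD 1.1). All effect and variance inputs are assumptions. The comparison can still be tested, so this is a correction to make, not a fatal fault.

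**What to change.** Replace the sentence in the Outcomes section with: *Change from before to after supplementation in vitamin D, hepcidin and ferritin levels will be tested with the paired t-test or, if the paired differences are not normally distributed, with the Wilcoxon signed-rank test.* A paired t-test on log levels, specified in advance, is a reasonable alternative for skewed markers and avoids choosing the test from a normality check in small groups.

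Delete McNemar's test and the reference to a proportion of events. If a proportion is wanted, keep McNemar's test only for a named binary outcome with its cut-off fixed before the data are seen.

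The cost is one sentence of protocol wording. Visits, blood samples and sample size do not change.
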